8.2.2 Special Assays

PK Samples

A maximum of 7 plasma PK samples per participant will be collected during the treatment and follow-up periods. PK blood samples will be obtained only if laboratory tests are being collected per routine medical care. Each blood sample will be limited to a volume of 250 µL. PK samples should not be drawn during infusions or during the flush. Caffeine plasma concentrations will be measured in the clinical laboratories at each site using a validated bioanalytical assay requiring 250 µL of whole blood for analysis. Therapeutic drug monitoring of caffeine per routine medical care can be performed at any time by the treating physician. This can replace a planned study sample. All information obtained from therapeutic drug monitoring of caffeine will be incorporated in the final data analysis, even if the time of collection does not follow the study collection schedule.

Epigenetic Samples

Epigenetic samples will be obtained from either leftover cellular components of plasma caffeine samples or whole blood samples scavenged from standard of care labs. A maximum of 2 samples will be collected per participant. The samples will be identified by a code number, and all other identifying information will be removed. A targeted epigenetic testing approach evaluating CpG methylation on genes encoding for cytochrome P450 enzymes involved in caffeine metabolism will be conducted and related to exposure. Once this testing is completed, any remaining epigenetic samples will be destroyed. Caregivers of participants will not be informed of epigenetic results.

8.3 Adverse Events and Serious Adverse Events

8.3.1 Definition of Adverse Events (AE)

An adverse event (AE) is any untoward medical occurrence in humans, whether or not considered drug-related, which occurs during the conduct of a clinical trial. (Any change in clinical status, routine labs, x-rays, physical examinations, etc.), that is considered clinically significant by the study investigator is considered an AE.

8.3.2 Definition of Serious Adverse Events (SAE)

A serious adverse event (SAE) as determined by the investigator is any event that results in any of the following outcomes:

1. Death
2. Life-threatening AE (“life-threatening” means that the study participant was, in the opinion of the investigator or sponsor, at immediate risk of death from the reaction as it occurred and required immediate intervention)
3. Persistent or significant incapacity or substantial disruption of the ability to conduct normal life functions
4. Inpatient hospitalization or prolongation of existing hospitalization
5. Important medical event that may not result in one of the above outcomes, but may jeopardize the health of the study participant or require medical or surgical intervention to prevent one of the outcomes listed in the above definition of serious event

8.3.3 Classification of an Adverse Event

8.3.3.1 Severity of Event

The investigator should use the following definitions when assessing severity of an adverse event:

1. **MILD:** Participant is aware of symptoms or has minor findings but tolerates them well, and no or minimal intervention required
2. **MODERATE:** Participant experiences enough symptoms or findings to require intervention
3. **SEVERE:** Participant experiences symptoms or findings that require significant intervention

8.3.3.2 Relationship to Study Intervention

All adverse events (AEs) must have their relationship to study intervention assessed by the clinician who examines and evaluates the participant based on temporal relationship and his/her clinical judgment. The degree of certainty about causality will be graded using the categories below. In a clinical trial, the study product must always be suspect.

- **Related** – The AE is known to occur with the study intervention, there is a reasonable possibility that the study intervention caused the AE, or there is a temporal relationship between the study intervention and event. Reasonable possibility means that there is evidence to suggest a causal relationship between the study intervention and the AE.

- **Not Related** – There is not a reasonable possibility that the administration of the study intervention caused the event, there is no temporal relationship between the study intervention and event onset, or an alternate etiology has been established.

The investigator will use the following question when assessing causality of an adverse event to study drug, where an affirmative answer designates the event as a suspected adverse reaction: Is there a reasonable possibility that the drug caused the event? “Reasonable possibility” means that there is evidence to suggest a causal relationship between the drug and the adverse event.

8.3.3.3 Expectedness

The investigator will be responsible for determining whether an adverse event (AE) is expected or unexpected. An AE will be considered unexpected if the nature, severity, or frequency of the event is not consistent with the risk information previously described for the study intervention.

8.3.4 Time Period and Frequency for Event Assessment and Follow-up

The occurrence of an adverse event (AE) or serious adverse event (SAE) may come to the attention of study personnel during the 7 day follow-up period.

All AEs including local and systemic reactions not meeting the criteria for SAEs will be captured on the appropriate case report form (CRF). Information to be collected includes event description, time of onset, clinician's assessment of severity, relationship to study product (assessed only by those with the training and authority to make a diagnosis), and time of resolution/stabilization of the event. All AEs occurring while on study must be documented appropriately regardless of relationship. All AEs will be followed to adequate resolution.

Any medical condition that is present at the time that the participant is screened will be considered as baseline and not reported as an AE. However, if the study participant's condition deteriorates at any time during the study, it will be recorded as an AE.

Changes in the severity of an AE will be documented to allow an assessment of the duration of the event at each level of severity to be performed. AEs characterized as intermittent require documentation of onset and duration of each episode.

The investigator will record all reportable events with start dates occurring any time after informed consent is obtained until time of discharge from the initial hospitalization.

8.3.5 Adverse Event Reporting

All reportable events as defined above, determined to be an AE based on physical examination, laboratory findings, or other means, will be reported in the electronic case report form (e-CRF) in the REDCap (Research Electronic Data Capture) database platform. The investigator will provide the date of onset and resolution, intensity, frequency, action(s) taken, changes in study drug dosing, relationship to study drug, and outcome.

8.3.6 Serious Adverse Event Reporting

The study clinician will immediately report to the investigator any serious adverse event, whether or not considered study intervention related, including those listed in the protocol or investigator brochure and must include an assessment of whether there is a reasonable possibility that the study intervention caused the event. Study endpoints that are serious adverse events (e.g., all-cause mortality) must be reported in accordance with the protocol unless there is evidence suggesting a causal relationship between the study intervention and the event (e.g., death from anaphylaxis).

All serious adverse events (SAEs) will be followed until satisfactory resolution or until the investigator deems the event to be chronic or the participant is stable.

The investigator will be responsible for notifying the Food and Drug Administration (FDA) of any unexpected fatal or life-threatening suspected adverse reaction as soon as possible, but in no case later than 7 calendar days after the sponsor's initial receipt of the information. In addition, the sponsor must notify FDA and all participating investigators in an Investigational New Drug (IND) safety report of potential serious risks, from clinical trials or any other source, as soon as possible, but in no case later than 15 calendar days after the sponsor determines that the information qualifies for reporting.

8.3.7 Reporting Events to Participants

Not applicable

8.3.8 Events of Special Interest

1. Seizures will be defined by the receipt of > 1 AED, as we are interested in identifying seizures which are difficult to control.
2. Necrotizing Enterocolitis - Bell Stage II or III⁵⁷

8.3.9 Reporting of Pregnancy

Not applicable

8.4 Unanticipated Problems

8.4.1 Definition of Unanticipated Problems (UP)

The Office for Human Research Protections (OHRP) considers unanticipated problems involving risks to participants or others to include, in general, any incident, experience, or outcome that meets all of the following criteria:

- Unexpected in terms of nature, severity, or frequency given (a) the research procedures that are described in the protocol-related documents, such as the Institutional Review Board (IRB)-approved research protocol and informed consent document; and (b) the characteristics of the participant population being studied;

- Related or possibly related to participation in the research (“possibly related” means there is a reasonable possibility that the incident, experience, or outcome may have been caused by the procedures involved in the research); and
- Suggests that the research places participants or others at a greater risk of harm (including physical, psychological, economic, or social harm) than was previously known or recognized.

8.4.2 Unanticipated Problem Reporting

The investigator will report unanticipated problems (UPs) to the reviewing Institutional Review Board (IRB). The UP report will include the following information:

- Protocol identifying information: protocol title and number, PI’s name, and the IRB project number;
- A detailed description of the event, incident, experience, or outcome;
- An explanation of the basis for determining that the event, incident, experience, or outcome represents an UP;
- A description of any changes to the protocol or other corrective actions that have been taken or are proposed in response to the UP.

To satisfy the requirement for prompt reporting, UPs will be reported using the following timeline:

- UPs that are serious adverse events (SAEs) will be reported to the IRB within 7 days of the investigator becoming aware of the event.
- Any other UP will be reported to the IRB within 30 days of the investigator becoming aware of the problem.

All UPs should be reported to appropriate institutional officials (as required by an institution’s written reporting procedures), the supporting agency head (or designee), and the Office for Human Research Protections (OHRP) within 30 days of the IRB’s receipt of the report of the problem from the investigator.

8.4.3 Reporting Unanticipated Problems to Participants

Not applicable

9 STATISTICAL CONSIDERATIONS

9.1 Statistical Hypotheses

- **Pharmacokinetics**

We hypothesize that drug clearance will be $\geq 20\%$ lower than expected for gestational age and birth weight as a result of HIE and therapeutic hypothermia.

- **Safety**

We hypothesize that frequency of seizures in both treatment cohorts will be within 20% of published results of neonates treated with therapeutic hypothermia in the NICHD Total Body Hypothermia for Neonatal Encephalopathy trial.⁵

- **Preliminary effectiveness**

We hypothesize that the risk ratio for an abnormal MRI prior to discharge will be favorable, i.e., between 0.7 and 1.1 in treated neonates compared to published results of neonates treated with therapeutic hypothermia in the NICHD Total Body Hypothermia for Neonatal Encephalopathy trial.⁵

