1 PROTOCOL SUMMARY

1.1 Synopsis

Title:	Pharmacokinetics and Safety of Caffeine in Neonates with Hypoxic-Ischemic Encephalopathy
Study Description:	This is a phase I, open-label, dose-escalating pharmacokinetics (PK) and safety study of caffeine in neonates with hypoxic-ischemic encephalopathy undergoing therapeutic hypothermia. We hypothesize that drug clearance will be $\geq 20\%$ lower than expected for gestational age and birth weight and that the incidence of adverse events will be within 20% of published results of neonates treated with therapeutic hypothermia in the NICHD Total Body Hypothermia for Neonatal Encephalopathy trial.
Objectives:	
Primary Objective: Characterize the PK of caffeine in neonates undergoing therapeutic hypothermia for hypoxic-ischemic encephalopathy (HIE).
 
Secondary Objectives: Characterize the safety of caffeine in neonates undergoing therapeutic hypothermia for HIE. Evaluate the preliminary effectiveness of caffeine in reducing brain injury in neonates with HIE.

Endpoints:	
Primary Endpoint: PK: Caffeine clearance
 
Secondary Endpoints: Safety: Adverse events Note: Seizures and necrotizing enterocolitis will be AEs of special interest Preliminary effectiveness: Death, abnormal MRI findings, neurodevelopment at 18-24 months

Study Population:	
Inclusion Criteria
 
 1. Documented informed consent from parent or guardian 2. ≥ 36 weeks gestational age at birth 3. Receiving therapeutic hypothermia for a diagnosis of HIE 4. Intravenous (IV) access 5. Postnatal age < 24 hours 
Exclusion Criteria
 
 1. Receiving > 1 anti-epileptic drug for seizures 2. Sustained (>4 hours) heart rate > 180 beats per minute 3. Known major congenital anomaly 4. Any condition which would make the participant, in the opinion of the investigator, unsuitable for the study
Phase:	1
Description of Sites/Facilities Enrolling Participants:	Up to 3 US Neonatal Intensive Care Units, including The University of North Carolina at Chapel Hill Newborn Critical Care Center

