4 STUDY DESIGN

4.1 Overall Design

This is a phase I, open-label, dose-escalating PK and safety study of caffeine in neonates with HIE undergoing therapeutic hypothermia. There will be two cohorts, with two caffeine dosing regimens (see **Section 6.1.2, Dosing and Administration**). Each cohort will consist of 9 neonates and the intervention duration will be 48 hours. An interim safety analysis will be conducted following the follow-up period in the final cohort 1 participant (see **Section 9.4.4, Safety Analyses**) to assess for safety prior to enrollment in cohort 2. We hypothesize that drug clearance will be $\geq 20\%$ lower than expected for gestational age and birth weight and that the incidence of adverse events will be similar to those in published trials of therapeutic hypothermia.

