9.2 Sample Size Determination

- **Pharmacokinetics**

A sample size of 9 neonates in each dosing cohort will be powered ($\geq 80\%$) to target a 95% confidence interval within 60% and 140% of the geometric mean estimate of clearance (assuming 36% between subject variability in clearance, which is based on existing literature of caffeine PK in neonates).⁵⁸⁻⁶⁰

- **Safety**

The frequency of seizures in the treated group of the NICHD trial was $\sim 40\%$.⁵ Estimation of the probability of seizures in our study will be based on the combined sample of 18 patients. For comparison with historical data, the null hypothesis that the frequency of seizures is 40% will be rejected if 11 or more adverse events (in 18 patients) are observed. The event probability will be no wider than 21% on each side of the point estimate and this will provide a power of 86%. The alternative hypothesis is that the frequency of seizures is $> 61\%$ or $< 19\%$ in our study (i.e., $> 21\%$ on either side of the point estimate of 40%).

- **Preliminary effectiveness**

This is an exploratory aim and will not be sufficiently powered to detect a significant reduction in brain injury on MRI. However, we estimate that there will be a trend toward risk reduction of brain injury in enrolled neonates compared to treated neonates in the NICHD trial.

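### The safety hypothesis is closeness to the historical seizure rate, but the only test can refute it and never support it, and no 95% interval from 18 infants fits within 20 points of 40%

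*Combined protocol and SAP*

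**What the plan says.** The hypothesis appears in three places. Section 9.1 (Safety) says: "We hypothesize that frequency of seizures in both treatment cohorts will be within 20% of published results of neonates treated with therapeutic hypothermia". The Synopsis (Section 1.1) widens it to all adverse events: "the incidence of adverse events will be within 20% of published results". Section 4.1 sets no margin and expects that "the incidence of adverse events will be similar to those in published trials of therapeutic hypothermia".

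The test is in Section 9.2 (Safety). It puts the historical frequency at about 40% and says that "the null hypothesis that the frequency of seizures is 40% will be rejected if 11 or more adverse events (in 18 patients) are observed". The alternative is a frequency above 61% or below 19%. The precision statement is "The event probability will be no wider than 21% on each side of the point estimate", with a stated power of 86%. No significance level or confidence level is given. The sample is pooled: "Estimation of the probability of seizures in our study will be based on the combined sample of 18 patients".

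Sections 9.4.1 and 9.4.4 plan counts and percentages of adverse events and a correlation of caffeine exposure with seizures and necrotizing enterocolitis. Neither contains an equivalence test or an interval criterion for the 20% margin. Section 9.4.4.1 defines a seizure event as receipt of more than one anti-epileptic drug.

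**The concern.** The claim that the sponsor hopes to make lies inside the null hypothesis. Rejecting 40% would count against it. Not rejecting 40% leaves it unproved, because a sample of 18 also fails to reject when the rate is far from 40%. The documents name no other route from the data to the hypothesis.

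The stake is the study's safety statement. Seizure is an event of special interest because caffeine may lower the seizure threshold (Section 3), and Section 4.2 presents the study as the first step towards a larger trial. If the report says that seizures were similar to published cooling results, later investigators may rely on a conclusion that the design cannot reach.

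Two smaller gaps add to this. The rejection rule counts adverse events where a binomial rule needs infants. The Synopsis extends the margin to adverse events in general, for which no comparison is planned.

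**Working it through.** **Inputs.** n = 18 (9 + 9), null rate 0.40, reject if X ≥ 11, alternative 0.61 on the upper side, precision 21 points, power 86%: all from Section 9.2. Margin 20%: Section 9.1. The scale of the margin is not stated, so both readings are checked:

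- percentage points: 40 ± 20, i.e. 20% to 60%;
- relative: 40 ± 0.20 × 40 = 40 ± 8, i.e. 32% to 48%.

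The historical 40% is treated as known exactly, which favours the plan.

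**1. The plan's own figures.**

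Precision: the Wilson half-width is z·√[p(1−p)/n + z²/(4n²)] / (1 + z²/n). It is largest at 9/18. With z = 1.96 it is 1.96 × √(0.01389 + 0.00296) / 1.2134 = 0.210. So 21% is reproduced as the largest 95% Wilson half-width. The largest exact (Clopper-Pearson) 90% half-width, 0.209, also matches.

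Power: P(X ≥ 11 | 0.40) = 0.058 is the one-sided level that the rule implies, and P(X ≥ 11 | 0.61) = 0.598. The stated 86% is not reproduced at 61%; the rule reaches it at a true rate of about 70%.

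**2. Can any result show closeness?** For each X from 0 to 18, I checked whether the interval lies wholly inside the window.

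| Interval | Counts inside 20–60% | 7/18 gives |
|---|---|---|
| 95% exact | none | 17.3–64.3% |
| 95% Wilson | none | 20.3–61.4% |
| 95% Wald | none | 16.4–61.4% |
| 95% Agresti-Coull | none | 20.2–61.5% |
| 95% Jeffreys | none | 19.4–61.7% |
| 90% exact | none | 19.9–60.8% |
| 90% Wilson | 7 only | 22.7–58.0% |
| 90% Agresti-Coull | 7 only | 22.6–58.1% |
| 90% Jeffreys | 7 only | 22.1–58.1% |

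P(X = 7 | n = 18, p = 0.40) = 0.189. So even under the methods that admit one result, it would occur in 19% of trials whose true rate is exactly 40%.

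Two one-sided exact tests at 5% agree with the exact interval. At 7/18, P(X ≥ 7 | 0.20) = 0.051 and P(X ≤ 7 | 0.60) = 0.058, and both would have to be at most 0.05.

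On the relative reading (32% to 48%), no count passes by any of these methods. With 9 infants, if each cohort were judged alone as Section 9.1 may be read, no count passes either.

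**3. What does non-rejection convey?** The rule does not reject for X = 0 to 10, i.e. observed rates from 0% to 10/18 = 56%. At 10/18 the exact 95% interval is 30.8% to 78.5%. At the plan's own upper alternative, P(X ≤ 10 | 0.61) = 1 − 0.598 = 0.402.

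**4. Scale of the gap.** An exact equivalence test with a 20-point margin and a true rate of 40% needs about 55 infants for 80% power (5% per side) or 66 (2.5% per side). With the relative margin it needs about 337 or 407.

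**The case against.** The strongest defence is that this is a secondary objective of a phase I pharmacokinetic study, and that Section 9.2 already speaks of estimating the seizure probability with a stated precision. That stands as far as it goes, and it lowers the severity. But the same section also sets a formal null, a threshold and a power, and none of these matches the hypothesis in Section 9.1. The interval method, its level and its interpretation are missing.

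A reader might infer more than the documents support:

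- That the plan will read non-rejection as similarity. No section says so. The plan is silent on what 10 or fewer of 18 would mean. At the low end such a reading would sit badly with the plan, because 0 to 3 of 18 (0% to 17%) fall in the stated alternative below 19%.
- That a 21-point precision against a 20-point margin settles the matter. It does not, since 21% is an upper bound. The count-by-count check is what carries the point.
- That no result of any kind could show closeness. That is true at 95% and for exact 90% intervals. Three 90% methods admit 7/18, and Section 9.2 states no level.
- That dose escalation rests on this test. It does not. Sections 9.4.4 and 10.1.6 give that decision to the independent safety monitor, and the test pools both cohorts.

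The reference to adverse events in the rejection rule is probably a slip, since the seizure definition is a yes-or-no event per infant. It still needs correcting.

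**Conclusion.** The point holds. The stated hypothesis is closeness, the only test has closeness as its null, and there is no criterion for concluding it. At 95% no count in 18 infants would place the rate within 20 points of 40%. A non-rejected result is compatible with rates up to 79% at 10/18, and the rule misses a true 61% about 40% of the time.

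This rests on three assumptions: the margin is in percentage points (the relative reading is stricter), the historical rate is a fixed 40%, and a claim of closeness requires the whole interval to lie inside the margin.

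The severity is should-fix. The objective is secondary and no escalation decision depends on it, but the reported safety conclusion does.

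**What to change.** In Sections 9.1 and 9.2, replace the hypothesis with an estimation objective: the number and proportion of infants (not adverse events) with seizures as defined in Section 9.4.4.1, with an exact 95% confidence interval, shown beside the historical rate. Change Sections 1.1 and 4.1 to match, dropping the 20% margin and the claim of similarity. Removing the margin is better than keeping one that 18 infants cannot meet.

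If the 11-of-18 rule is kept, present it only as a flag for an excess of seizures, and state that 10 or fewer of 18 is not evidence of similarity.

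The cost is wording: no more infants and no change in conduct. The price is a less favourable safety statement. The change should be made before the seizure data are analysed.

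### The 20% seizure margin in 1.1 and 9.1 has no scale and does not match the 19% to 61% range tested in 9.2, so the plan can support contradictory safety statements

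*Combined protocol and SAP*

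**What the plan says.** The safety hypothesis appears in four places of the combined protocol and SAP, in different terms.

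- **9.1, Safety:** "We hypothesize that frequency of seizures in both treatment cohorts will be within 20% of published results", the published results being those of the cooled infants in the NICHD trial. No scale is given, and the margin is attached to both cohorts.
- **1.1 Synopsis:** the same 20% is applied to every adverse event: "the incidence of adverse events will be within 20% of published results of neonates treated with therapeutic hypothermia".
- **4.1 Overall Design:** no number at all: "the incidence of adverse events will be similar to those in published trials of therapeutic hypothermia".
- **9.2, Safety:** the reference is a seizure frequency of about 40%, and "Estimation of the probability of seizures in our study will be based on the combined sample of 18 patients". The decision rule is that "the null hypothesis that the frequency of seizures is 40% will be rejected if 11 or more adverse events (in 18 patients) are observed". The section adds: "The event probability will be no wider than 21% on each side of the point estimate and this will provide a power of 86" per cent. The alternatives are above 61% or below 19%, which it explains as more than 21% "on either side of the point estimate of 40" per cent.

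Nothing in 9.2 says that its 21 points define the 20% margin of 9.1, and no section justifies the width.

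**The concern.** A 20% margin around a reference of 40% can mean 32% to 48% (relative) or 20% to 60% (percentage points). Section 9.2 works in percentage points but with 21. The clearance hypothesis directly above the safety hypothesis in 9.1 uses a 20% that is plainly relative, so a reader could carry that scale over.

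Seizures are an adverse event of special interest because of the stated concern about a lowered seizure threshold (section 3). What is at stake is the sentence the trial may write about them. A report that seizures stayed within 20% of the historical rate could be taken as relative, while the only limits the protocol writes out reach about one and a half times that rate. The pooled test in 9.2 also does not match a hypothesis stated for both cohorts.

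**Working it through.** **Inputs.** Reference rate 40%, n = 18, rejection at X ≥ 11, alternatives 19% and 61%, stated power 86% (all 9.2); margin 20% (1.1 and 9.1). All probabilities are exact binomial.

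**1. The plan's own power figure.** Power = P(X ≥ 11 | n = 18, p).
- p = 0.40: 0.058. This is the one-sided type I error; 9.2 states no alpha.
- p = 0.61: 0.598, against the stated 86%.
- p = 0.70: 0.859. With this cut-off, 86% is reached only at a true rate of about 70%.

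Cut-offs of 10, 12 and 13 give 0.765, 0.408 and 0.235 at 61%. Normal approximations at one-sided 5% or 10% give 0.47 to 0.71. None reproduces 86% at 61%. The rule has no lower cut-off, so it does not test the 19% alternative. Adding a rejection region of X ≤ 3 would give power 0.545 at 19%.

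The 21-point precision figure does have a match: 0.210 is the half-width of a 95% Wilson interval at 9 of 18.

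**2. The possible margins.**
- Relative 20%: 0.40 × 0.8 = 32% to 0.40 × 1.2 = 48%.
- 20 percentage points: 20% to 60%.
- Section 9.2, 21 percentage points: 19% to 61%. The upper limit is 0.61 / 0.40 = 1.525 times the reference.

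In counts of 18:
- Relative: 0.32 × 18 = 5.76 and 0.48 × 18 = 8.64, so 6 to 8 events.
- 20 points: 3.6 and 10.8, so 4 to 10 events.
- 21 points: 0.19 × 18 = 3.42 and 0.61 × 18 = 10.98, also 4 to 10 events.

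The gap between 20 and 21 points is therefore one of consistency and does not change which counts fall inside. The gap between relative and percentage points does.

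**3. Can the 9.2 rule serve a relative margin?** P(X ≥ 11 | 18, 0.48) = 0.190. At the upper relative limit the rule fails to reject 81% of the time.

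**4. Where the plan contradicts itself.** With 9 of 18 (50%) or 10 of 18 (56%), X < 11, so 40% is not rejected. Both rates lie inside 19% to 61% and above 48%.

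**5. What non-rejection shows.** Exact (Clopper-Pearson) 95% CIs:

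| Events of 18 | Rate | 95% CI |
|---|---|---|
| 6 | 33% | 13% to 59% |
| 7 | 39% | 17% to 64% |
| 8 | 44% | 22% to 69% |
| 9 | 50% | 26% to 74% |
| 10 | 56% | 31% to 78% |

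The upper limit is below 61% only with 6 or fewer events, and the lower limit is above 19% only with 8 or more. So no count out of 18 gives an interval wholly inside 19% to 61%.

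**The case against.** The strongest reply is that 9.2 already settles the matter. It gives a numerical rule on an explicit scale and itself writes 21% for percentage points, and 9.1 names a risk ratio where it wants a relative comparison of proportions (the MRI hypothesis). That makes percentage points a reasonable inference. It remains an inference: the number differs, 9.2 does not refer back to 9.1, and 1.1 applies the margin to events for which 9.2 gives no reference rate.

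A second reply concerns stakes. Safety is a secondary objective, and the review before cohort 2 and the trigger for a halt rest on the independent safety monitor and the count of drug-related SAEs (9.4.4, 10.1.6), not on this margin. That stands. The effect is on what may be concluded and reported.

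Two stronger readings are tempting, and the documents do not support them.

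- A reader might infer that the missing scale is why a 1.5-fold rate escapes detection. At a true rate of 60%, P(X ≤ 10) = 0.437, a 44% miss. That figure comes from n = 18 and the cut-off of 11 and is the same on either scale.
- A reader might compute how often the two margins disagree: counts of 4, 5, 9 or 10 have probability 0.38 at a true rate of 40%. That treats whether the observed rate falls inside a band as the decision rule, which the plan never says. The low counts also raise no safety concern.

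**Conclusion.** The point holds as an inconsistency in how the safety hypothesis is stated and what it can support. Sections 1.1 and 9.1 leave the scale open, and 9.2 uses percentage points with another number. At 9 or 10 events of 18 the plan allows both that 40% was not rejected and that the rate is outside a relative 20% margin. The 9.2 rule cannot back a relative margin (19% rejection at 48%). On any scale, non-rejection does not show that the rate lies inside it.

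The stated 86% power is about 60% at the 61% limit.

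These figures assume a reference of exactly 40%, all 18 infants analysed and independent outcomes. The point should be corrected, but it does not affect the primary PK objective or the safety monitor's triggers.

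**What to change.** 1. **9.1:** state the seizure margin in percentage points with the limits of 9.2 (19% to 61%, i.e. 40% plus or minus 21 points). Note that the upper limit is about 1.5 times the historical rate, and say that the margin applies to the pooled 18 infants, as in 9.2.
2. **1.1 and 4.1:** refer to the seizure hypothesis in 9.1. Remove the 20% claim and the claim of similarity for all adverse events, since 9.2 gives a reference rate for seizures only. The 40% should not be carried into a sentence about all adverse events.
3. **Reporting:** give the observed seizure rate with its exact 95% CI. Do not describe 10 or fewer events as being within the margin unless the interval lies inside it. At n = 18 no count meets that, so the report should say that 40% was not rejected and show the interval.
4. **9.2:** restate the power at the chosen limit. The 11-of-18 rule has about 60% power at 61%. Say also that the rule acts on the upper side only, or add a lower cut-off.

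Cost: edits in four sections and a less reassuring safety statement. No extra data or patients are needed.
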